4. INVESTIGATIONAL PLAN

4.1. Overall Study Design

This is an open-label monotherapy study of INCB054828 in subjects with metastatic or surgically unresectable urothelial cancer harboring FGF/FGFR alterations. Subjects will receive INCB054828 at a QD starting dose of 13.5 mg on a 2-weeks-on-therapy and 1-week-off-therapy schedule (Figure 4).

Protocol Amendment 5 introduces a new dose regimen for INCB054828 (13.5 mg continuous dose regimen [no planned dose holiday]). Subjects receiving a continuous dose regimen will be enrolled in a new cohort (Cohort A-CD). *Note:* Subjects enrolled in the current Cohort A (intermittent dose regimen [Cohort A-ID]) will continue to receive treatment with INCB054828 as 2-weeks-on/1-week-off therapy. Subjects in Cohort A-ID will not switch to a continuous dose regimen.

Complete study drug administration information can be found in Section 5.2.1.

Subjects can enroll if they have a known FGF/FGFR alteration and have either: (a) failed at least 1 previous treatment for their metastatic or surgically unresectable urothelial carcinoma (ie, chemotherapy, immunotherapy), or (b) have not received chemotherapy for metastatic or surgically unresectable urothelial carcinoma due to poor performance status (ie, ECOG performance status of 2) and have insufficient renal function (ie, creatinine clearance < 60 mL/min or local guidelines). Subjects may have undergone cystectomy.

Potential subjects can be screened/enrolled based on local genomic sequencing but must have their tumor samples sequenced through the sponsor's central laboratory. The results from the central laboratory will be considered final. In cases where the central laboratory does not show an alteration, the investigator will decide if continuing treatment is in the best interest of the subject; however, the subject will not be included in the efficacy analyses and may be replaced.

The study will enroll approximately 240 subjects:

[figure not shown]
- Cohort A-ID: FGFR3 mutations or fusions (n = 100); this cohort will complete enrollment before Cohort A-CD begins enrolling subjects.
- Cohort A-CD: FGFR3 mutations or fusions (n = 100)
- Cohort B: all other FGF/FGFR alterations (n = 40)

Once a subject has completed screening and has enrolled into the study, treatment will start on Day 1. Subjects will undergo routine safety assessments during treatment as well as routine efficacy assessments.

Subjects will be allowed to continue receiving study drug in 21-day cycles until documented disease progression or unacceptable toxicity is reported.

In addition to introducing continuous dosing, up-titration will be implemented. Any subject who does not reach the target serum phosphate level of > 5.5 mg/dL will increase the daily dose to 18mg.

Figure 4: Study Design

4.2. Measures Taken to Avoid Bias

This is an open-label study; no comparisons will be made between subjects. Measurements of safety and efficacy are objective measurements, and only comparisons to pretreatment conditions will be made.

4.3. Number of Subjects

Approximately 240 subjects will be enrolled in this study. Subjects will be enrolled from up to 100 sites globally.

4.4. Duration of Treatment and Subject Participation

Subjects without a genomic sequencing report will sign a consent form to allow tissue samples to undergo sequencing to determine FGF/FGFR alteration at the sponsor's central laboratory. The process will take approximately 2.5 weeks. Subjects whose genomic profiling has been completed at the sponsor's central laboratory within the past 2 years will not need to be sequenced again.

Once FGF/FGFR alteration status is confirmed, the subject will sign the study ICF. After signing the ICF, screening assessments may be completed over a period of up to 28 days. Each subject enrolled in the study may continue to receive study treatment in continuous 21-day cycles as long as the subject is receiving benefit and has not met any criteria for study withdrawal. If the subject discontinues INCB054828, the treatment period will end and the subject will enter the follow-up period (see Section 6.4). Study participation is expected to average approximately 6 months per individual subject.

4.5. Overall Study Duration

The study begins when the first subject signs the study informed consent form. The end of the study will occur when all subjects have discontinued study drug and/or have completed applicable follow-up assessments.

A database lock of the study may occur to allow the analysis of the study data while any enrolled subjects remain ongoing, as long as the Week 21 assessments have been completed for the last subject enrolled. Any remaining subjects may continue to receive study treatment and be seen by the investigator per usual standard of care for this population. The investigator will be expected to monitor for and report any SAEs, AEs of special interest, and pregnancies, as detailed in Section 8. The remaining subjects are considered to be on study until a discontinuation criterion is met and written notification is provided to the sponsor.

4.6. Study Termination

The investigator retains the right to terminate study participation at any time, according to the terms specified in the study contract. The investigator/head of study site (Japan) is to notify the institutional review board (IRB)/independent ethics committee (IEC) in writing of the study's completion or early termination, send a copy of the notification to the sponsor or sponsor's designee, and retain 1 copy for the site study regulatory file.

The sponsor may terminate the study electively, if required by regulatory decision. If the study is terminated prematurely, the sponsor will notify the investigators/head of the study site (Japan), the IRBs and IECs, and regulatory bodies of the decision and reason for termination of the study.

Japan: The head of the study site will notify the investigators and the IRBs of the decision and reason for termination of the study.

5. TREATMENT

5.1. Treatment Assignment

5.1.1. Subject Numbering and Treatment Assignment

Study sites will enter subject demographic and baseline data into the Interactive Response Technology (IRT) in order to receive a subject number and treatment allocation.

All subject numbers will be 6 digits; the first 3 digits will be the site number and the last 3 digits will be the subject's number. This subject number will be maintained throughout the study and will not be reassigned. Subjects who withdraw consent or discontinue from the study after being assigned a subject number will retain their initial number.

The investigator or designee will pull the correct number of bottles of study drug from their stock and dispense the study drug to the subject.

Japan: The head of the study site is responsible for ensuring study drug accountability. The head of the study site can delegate the control of and accountability for the study drug to an investigational product storage manager. Site staff will contact the IRT to obtain the initial study drug assignment. The head of the study site or the investigational product storage manager will obtain the required number of study drug bottles from their stock that correspond to the dose and dispense the study drug to the subject.

All subsequent dispensing of study drug should follow this process. Refer to the IRT manual for detailed information.

For subjects who signed an ICF but are not allocated and for subjects who are allocated but were not treated, refer to the electronic case report form (eCRF) Completion Guidelines for instruction on which eCRFs to complete.

5.1.2. Randomization and Blinding

Not applicable. This is an open-label study. Subjects will be enrolled in succession.

5.2. INCB054828

The following describes the study drug used in this study. Additional details of handling, packaging, and labeling of the study drug will be defined in a separate Manual of Procedures.

5.2.1. INCB054828 Description and Administration

INCB054828 will be self-administered as a QD oral treatment on a 21-day cycle. Subjects will take study drug for 2 weeks continuously (14 days) followed by a 1-week (7 days) break. The

starting dose will be 13.5 mg. Protocol Amendment 5 introduces a new dose regimen for INCB054828 (13.5 mg continuous dose regimen [no planned dose holiday]). Subjects receiving a continuous dose regimen will be enrolled in a new cohort (Cohort A-CD). *Note:* Subjects enrolled in the current Cohort A (intermittent dose regimen [Cohort A-ID]) will continue to receive treatment with INCB054828 as 2 weeks-on/1 week off. Subjects in Cohort A-ID will not switch to a continuous dose regimen.

Each dose of study drug should be taken as soon as possible upon rising, with or without food.

5.2.2. Supply, Packaging, and Labeling

Study drug will be supplied as 2 mg and 4.5 mg tablets. All tablet excipients comply with the requirements of the applicable compendial monographs (Ph Eur, USP-NF; refer to the [IB](#)). INCB054828 tablets will be packaged in high-density polyethylene bottles. No preparation is required.

All Incyte investigational product labels will be in the local language and will comply with the legal requirements of each country.

5.2.3. Storage

Bottles of tablets should be stored at room temperature, 15°C to 30°C (59°F to 86°F).

5.2.4. Instruction to Subjects for Handling Study Drug (INCB054828)

The subject must be instructed in the handling of study drug as follows:

- To store the study drug at room temperature.
- To only remove from the study drug bottle the number of tablets needed at the time of administration.
- Not to remove doses in advance of the next scheduled administration.
- Tablets cannot be split or crushed.
- To make every effort to take doses on schedule.
- To report any missed doses.
- To take study drug immediately upon rising with a glass of water; study drug can be taken with or without food.
- If the subject vomits after taking study drug, the subject should not take another dose that day.
- To keep study drug in a safe place and out of reach of children.
- To bring all used and unused study drug bottles to the site at each visit.
- If a dose of INCB054828 is missed by more than 4 hours, that dose should be skipped and the next scheduled dose should be administered at the usual time.

5.3. Treatment Compliance

Compliance with all study-related treatments should be emphasized to the subject by the site personnel, and appropriate steps should be taken to optimize compliance during the study. Compliance with INCB054828 will be calculated by the sponsor based on the drug accountability documented by the site staff and monitored by the sponsor/designee (tablet counts). Subjects will be instructed to bring all study drugs with them to the study visits in order for site personnel to conduct tablet counts to assess study drug accountability. The drug accountability documentation will be used by the sponsor to calculate treatment compliance.

5.4. Treatment Interruptions and Adjustments

5.4.1. Dose Modifications

Dose interruptions and modifications may occur for individual study subjects. The occurrence of toxicities (related or unrelated to study drug) will guide decisions for treatment interruptions and discontinuation for individual subjects.

5.4.2. Criteria and Procedures for Dose Interruptions and Adjustments of Study Drug

Treatment with INCB054828 may be delayed up to 14 days to allow for resolution of toxicity. Subjects may resume treatment if no medical condition or other circumstance exists that, in the opinion of the investigator, would make the subject unsuitable for further participation in the study. The treating investigator should contact the sponsor to discuss the case of any subject whose treatment has been delayed for more than 14 days before restarting treatment with INCB054828.

For subjects who present with possible or confirmed serous retinal detachment/retinal pigmented epithelium detachment (SRD/RPED) based on OCT, the guidelines in [Table 2](#) should be followed. It is recommended to discuss the findings with the Incyte medical monitor before making changes to the subject's treatment.

Per CTCAE v4.03, retinal detachment is graded as Grade 3 (macular sparing) and Grade 4 (macula-off), but this refers to rhegmatogenous retinal detachment (when a hole occurs in the retina). There is no grading for SRD/RPED (there is no hole in the macula, just fluid accumulation). Therefore, grading should be based on retinopathy.

Because subjects may enter the study with extensive pretreatment toxicities, these dose reduction rules are provided as guidelines (see [Table 2](#)). Individual decisions regarding dose reduction should be made using clinical judgment and in consultation with the sponsor's medical monitor, taking into account relatedness of the AE to the study drug and the subject's underlying condition. Adverse events that have a clear alternative explanation or transient (≤ 72 hours) abnormal laboratory values without associated clinically significant signs or symptoms may be exempt from dose-reduction rules.

Table 2: Guidelines for Interruption and Restarting of Study Drug

ADVERSE EVENT	ACTION TAKEN
Chemistry	

 AST and/or ALT > 5.0 × ULN Note: In subjects with bone metastasis-related elevations at baseline, contact sponsor to discuss clinical management and possible dose reductions.	Step 1: Interrupt study drug up to 2 weeks (14 days) until the toxicity has resolved to ≤ Grade 1 except by approval of the medical monitor. Step 2: If assessed as related to study drug, restart study drug at the next lower dose; monitor as clinically indicated.
Other toxicities	

 Any Grade 1 or Grade 2 toxicity. 	Continue study drug treatment and treat the toxicity; monitor as clinically indicated.

 Any Grade 3 toxicity, if clinically significant and not manageable by supportive care. 	Step 1: Interrupt study drug up to 2 weeks (14 days), until toxicity resolves to ≤ Grade 1. Step 2: Restart study drug at same dose. If assessed as related to study drug, restart study drug at next lower dose; monitor as clinically indicated.

 Any recurrent Grade 3 toxicity after 2 dose reductions. 	Discontinue study drug administration and follow-up per Protocol. (Exceptions require approval of sponsor.)

 Any other Grade 4 toxicity. 	Discontinue study drug administration and follow-up per Protocol.

The sponsor recommends a maximum of 2 dose level reductions: subjects administered 13.5 mg can decrease to 9 mg and if additional dose reduction is required, subjects can decrease to 4.5 mg. Subjects enrolled before this amendment may have been reduced to 6 mg. The frequency of dosing (either intermittent or continuous) remains the same. A dose below 4.5 mg is not allowed.

For subjects who are up-titrated to 18 mg from 13.5 mg can be reduced back down to a dose of 13.5 mg, then 9 mg, then 4.5 mg. A dose below 4.5 mg is not allowed.

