5.4.3. Management of Hyperphosphatemia

Hyperphosphatemia is an expected on-target pharmacologic effect of FGFR inhibition. Hyperphosphatemia should be managed with diet modifications, phosphate binders and diuretics, or a dose reduction per the recommendations in [Table 3](#). **Note for Japan:** Phosphate binders are not approved for the treatment of increases of serum phosphate caused by an FGFR inhibitor. When phosphate binders are used, the binders must be tracked in a drug accountability ledger that includes lot number. This drug accountability ledger will be monitored in the same way the study drug ledger is reviewed.

Table 3: Recommended Approach for Hyperphosphatemia Management

Serum Phosphate Level	Supportive Care	Guidance for Interruption/Discontinuation of INCB054828	Guidance for Restarting INCB054828
> 5.5 mg/dL and ≤ 7 mg/dL	Initiate a low-phosphate diet.	No action.	Not applicable.
> 7 mg/dL and ≤ 10 mg/dL	Initiate/continue a low-phosphate diet and initiate phosphate-binding therapy once serum phosphate level is > 7 mg/dL. Monitor serum phosphate at least twice a week and adjust the dose of binders as needed; continue to monitor serum phosphate at least twice a week until return to normal range.	If serum phosphate level continues to be > 7 mg/dL and ≤ 10 mg/dL with concomitant phosphate-binding therapy for 2 weeks, or if there is recurrence of serum phosphate level in this range, interrupt INCB054828 for up to 2 weeks (not including the planned dose interruption per treatment cycle).	Restart at the same dose when serum phosphate is < 7 mg/dL. If serum phosphate level recurs at > 7 mg/dL, restart INCB054828 with dose reduction.
> 10 mg/dL	Continue to maintain a low-phosphate diet, adjust phosphate-binding therapy, and start/continue phosphaturic agent. Continue to monitor serum phosphate at least twice a week until return to normal range.	If serum phosphate level is > 10 mg/dL for 1 week following phosphate-binding therapy and low phosphate diet, interrupt INCB054828. If there is recurrence of serum phosphate level in this range following 2 dose reductions, permanently discontinue INCB054828.	Restart INCB054828 at reduced dose with phosphate binders when serum phosphate is < 7 mg/dL.

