5.4.4. Up-Titration

Any subjects treated at 13.5 mg QD will be titrated up to 18 mg QD using their current dose regimen with approval from the medical monitor if they meet the following criteria:

- Have been on study drug for at least 1 cycle.
- Have been compliant with taking study drug.
- Have no ongoing Grade 2 or higher treatment-related AE.
- Have not achieved hyperphosphatemia defined as a serum phosphate level of > 5.5 mg/dL.

Subjects who are titrated up to 18 mg QD will begin the next cycle at the new dose level and must agree to all Cycle 1 assessments (████████ safety assessments [hematology and blood chemistry]). Up-titration may occur no earlier than Cycle 2 Day 1, so that subjects are observed for phosphate level and AEs for at least 1 cycle.

For subjects who are up-titrated from 13.5 mg to 18 mg, dose reductions are allowed (see Section 5.4.2).

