5.4.5. Criteria for Permanent Discontinuation of Study Drug

The occurrence of unacceptable toxicity not caused by the underlying malignancy will be presumed to be related to study drug treatment and will require that the study drug be permanently discontinued. Unacceptable toxicity is defined as follows:

- Occurrence of an AE that is related to treatment with the study drug that, in the judgment of the investigator or the sponsor's medical monitor, compromises the subject's ability to continue study-specific procedures or is considered to not be in the subject's best interest.
- An AE requiring more than 2 dose reductions (unless dose has been up-titrated, then 3 dose reductions are allowed).
- Persistent AE requiring a delay of therapy for more than 21 days unless a greater delay has been approved by the sponsor.
- Increase in QT/QTcF to > 500 milliseconds or to > 60 milliseconds over baseline.

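### After up-titration the protocol gives two different limits on dose reductions before study drug stops; its summary sentences also state up-titration without the conditions in Section 5.4.4

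*Protocol*

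**What the plan says.** **Number of reductions**

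- Table 2 (Protocol 5.4.2) discontinues drug for "Any recurrent Grade 3 toxicity after 2 dose reductions". It adds "Exceptions require approval of sponsor", and the text before the table describes its rules as guidelines to be used with clinical judgment.
- Table 3 (Protocol 5.4.3), in the row for phosphate above 10 mg/dL, calls for permanent discontinuation: "If there is recurrence of serum phosphate level in this range following 2 dose reductions". The row has no exception.
- The text beneath Table 2 recommends at most two reductions from 13.5 mg. It then says that subjects "up-titrated to 18 mg from 13.5 mg can be reduced back down to a dose of 13.5 mg, then 9 mg, then 4.5 mg". Nothing below 4.5 mg is allowed.
- Section 5.4.5 counts as unacceptable toxicity "An AE requiring more than 2 dose reductions (unless dose has been up-titrated, then 3 dose reductions are allowed". Section 5.5.1 lists unacceptable toxicity among the reasons for which a subject must come off drug.

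**Up-titration**

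- Protocol 4.1 says "Any subject who does not reach the target serum phosphate level of > 5.5 mg/dL will increase the daily dose to 18mg". The Synopsis and SAP Section 3 say the same.
- Section 5.4.4 makes the increase happen "with approval from the medical monitor if they meet the following criteria". The criteria are one cycle on drug, compliance, phosphate not above 5.5 mg/dL, and "Have no ongoing Grade 2 or higher treatment-related AE". The increase may not come before Cycle 2 Day 1.

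**The concern.** A site that has up-titrated a subject, reduced twice and then sees one of the two trigger events finds two answers in the same protocol. The tables tell it to stop; the ladder and Section 5.4.5 tell it that one more reduction is available. No order of precedence is given, and Section 5.4.5 feeds a mandatory withdrawal criterion. A site deciding whether to up-titrate can likewise find an unconditional instruction in the design sections and a conditional one in Section 5.4.4.

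The direct stake is consistent handling of individual subjects. The statistical stake is indirect. Exposure (SAP 6.4) and the counts of subjects with reductions or discontinuation because of adverse events (SAP 8.2.2) would partly reflect which page a site followed. SAP 5.3.2 builds the per-protocol population from a review of deviations and dose administration. That review cannot classify a third reduction, or a decision not to escalate, until one rule is settled.

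**Working it through.** The first check is a count of steps; the rest is a comparison of text.

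**Step 1. Reproduce the protocol's own counts.** Inputs: the dose levels in Section 5.4.2. Permitted reductions = number of dose levels − 1.

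- Never up-titrated: 13.5, 9, 4.5 mg, so 3 − 1 = 2. This matches the maximum of 2 in Section 5.4.2.
- Up-titrated: 18, 13.5, 9, 4.5 mg, so 4 − 1 = 3. This matches the 3 in Section 5.4.5.

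**Step 2. Dose reached after two reductions.**

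- Never up-titrated: 13.5 → 9 → 4.5 mg. The subject is at the floor, no third step exists, and all four passages agree.
- Up-titrated: 18 → 13.5 → 9 mg. One step remains on the ladder.

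The disagreement is therefore 3 − 2 = 1 step, for up-titrated subjects only.

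**Step 3. Set the passages side by side for an up-titrated subject at 9 mg after two reductions.**

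| Event | Table | Ladder in 5.4.2, and 5.4.5 |
|---|---|---|
| Grade 3 toxicity recurs | Table 2: discontinue, unless the sponsor approves an exception | Third reduction, to 4.5 mg, permitted |
| Phosphate > 10 mg/dL recurs | Table 3: discontinue permanently, no exception | Third reduction, to 4.5 mg, permitted |
| Phosphate > 7 and ≤ 10 mg/dL recurs | Table 3: dose reduction, no limit on their number | No conflict |

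The conflict is confined to the first two rows. It is softer in the first and firmer in the second. Because Table 2 and the ladder both sit in Section 5.4.2, that section is inconsistent within itself.

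**Step 4. Could the step from 18 to 13.5 mg be uncounted?** If it were a return to the starting dose, the tables' two reductions would be 13.5 → 9 → 4.5 mg and the gap would close. Section 5.4.5 does not count that way: it reaches 3 only by including that step. Nothing tells a site to count differently when using the tables.

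**Step 5. Up-titration.** Take subjects on 13.5 mg with phosphate not above 5.5 mg/dL after one cycle.

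- Compliant, no current related event of Grade 2 or worse: both texts lead to 18 mg, subject under 5.4.4 to the medical monitor's approval.
- Current related event of Grade 2 or worse: increased under Protocol 4.1, not under 5.4.4.
- Not compliant: increased under Protocol 4.1, not under 5.4.4.

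The three unconditional sentences carry no cross-reference. Section 4.1 sends the reader to Section 5.2.1 for full administration details, and 5.2.1 does not mention up-titration. However, the dispensing row of Table 4 and Section 1.3.2.1 both point to 5.4.4.

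**The case against.** **The tables are only guidance.** Table 2 is described as a guideline and allows sponsor-approved exceptions. Table 3 is presented as a recommended approach. Section 5.4.5 is the section that defines mandatory stopping, and it contains the up-titration clause. This stands as a softening for Table 2. It does not remove the conflict: by default Table 2 still stops drug one step before 5.4.5 requires it, and the row of Table 3 at issue calls for permanent discontinuation without any exception.

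**The texts can be read together.** Three reductions in 5.4.5 may be an overall ceiling, with the tables adding tighter triggers for two specific recurrent events. That reading is possible, but no passage states it. The tables' figure of two is also the number of steps open to a subject never up-titrated, so it can equally be read as a limit not adapted when 18 mg was added. The documents do not settle which.

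**Up-titration is a matter of summary against detail.** This largely stands. Section 5.4.4 is the dedicated procedure, Table 4 directs sites to it at dispensing, and the medical monitor must approve each increase. SAP Section 3 recaps the design and does not direct dosing. A reader might infer from the summary sentences that escalation is automatic; Section 5.4.4 rules that out. What remains is a literal mismatch in three places, with no pointer to the conditions.

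**Harm is not shown.** This also stands. The literal table reading stops drug earlier, and escalation needs approval. The point is that identical facts may be handled differently, not that either handling is shown to be unsafe.

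**Conclusion.** The point holds in a narrow form. For up-titrated subjects who have had two reductions, recurrent Grade 3 toxicity and recurrent phosphate above 10 mg/dL each meet conflicting instructions, one reduction apart. The unconditional up-titration sentences are a secondary inconsistency.

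The number of subjects affected is unknown and probably small, since each must be up-titrated, reduced twice and then have one of two specific recurrent events. Three stronger readings are not supported:

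- A reader might infer that the tables stop everyone after two reductions. They do so only for the two triggers, and for subjects never up-titrated the passages agree.
- A reader might size the problem from Protocol Table 1, where hyperphosphatemia was not reported in 50 − 38 = 12 of 50 (24%; exact 95% CI 13.1% to 38.2%) at 13.5 mg intermittent and in 15 − 14 = 1 of 15 (6.7%; 0.2% to 31.9%) at 13.5 mg continuous. These are at most possible candidates for up-titration, not subjects who would meet a conflict. They use reported adverse events in place of the laboratory criterion, and the continuous-dosing figure is very imprecise. Up-titration also arrived only with Amendment 6 (20 NOV 2018), after the Cohort A-ID futility analysis on about 45 subjects. No projection to this trial should be made from them.
- A reader might infer that the primary result is compromised. The primary ORR uses all subjects with a centrally known alteration and at least one dose. No one enters or leaves that population through this ambiguity, and the estimator is unchanged. The per-protocol ORR, a sensitivity analysis, is where the ambiguity could enter.

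**What to change.** 1. Reconcile Tables 2 and 3 with the ladder in Section 5.4.2 and with Section 5.4.5, so that one count of permitted reductions applies to up-titrated subjects for each trigger. If the tables are meant to be stricter for those two events, say so in the tables and in 5.4.5.
2. Reconcile the sentences in the Synopsis, Protocol 4.1 and SAP Section 3 with Section 5.4.4, for example by a cross-reference.
3. Once the rules are settled, record for the per-protocol review in SAP 5.3.2 how earlier decisions taken under either text will be classified, before the database freeze.

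Which clinical rule stands is for the sponsor to decide; this review takes no position.

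The cost is wording in two tables and three design paragraphs at the next amendment, a clarification letter to sites, and a short note for the per-protocol review. Sample size and the primary analysis do not change.
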